11.3 ADDITIONAL EFFICACY ANALYSES

The additional efficacy endpoints stated in section 4.3 will be analyzed using both the FAS.

11.3.1 Hb Correction and Maintenance

11.3.1.1 Time to achieve the first hemoglobin (Hb) response

Hemoglobin response is defined as the primary endpoint for the Ex-US submission and the first secondary endpoint for the US submission. It will be analyzed and compared between the 2 treatment groups using the Cox Proportional Hazards model adjusting for the above-

mentioned stratification factors. Non-inferiority of roxadustat vs. ESA will be tested. Non-inferiority will be declared if the upper bound of the 2-sided 95% confidence interval of the hazard ratio is less than 1.3. Subjects will be non-responder if the subject drop out the study early.

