- Mean change in mean arterial pressure (MAP) averaged over Weeks 8 to 12 will be analyzed using an MMRM model with baseline MAP as a covariate and treatment group, visit, visits by treatment arm, and randomization stratification factors as factors. Superiority will be declared if the lower bound of the two-sided 95% CI of the difference between epoetin alfa and roxadustat exceeds zero.

The time to achieve the first Hb response defined as the primary endpoint (for ex-US submission) will be analyzed using the Cox Proportional Hazards model adjusting for treatment group and other stratification factors. Non-inferiority of roxadustat vs. epoetin alfa will be tested. Non-inferiority will be declared if the upper bound of the two-sided 95% CI of the hazard ratio is less than 1.3.

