4.3 SECONDARY EFFICACY ENDPOINTS

The secondary efficacy endpoints are for both US and Ex-US submissions unless specified otherwise:

US (FDA submission): The proportion of subjects who achieve a Hb response at two consecutive visits with at least 5 days apart during the first 24 weeks of treatment, without rescue therapy within 6 weeks prior to the Hb response. This analysis will be based on the ITT Population.

A Hb response is defined, using central laboratory values, as

- Hb ≥ 11.0 g/dL and a Hb increase from baseline by ≥ 1.0 g/dL in subjects whose baseline Hb > 8.0 g/dL, or
- Increase in Hb ≥ 2.0 g/dL in subjects whose baseline Hb ≤ 8.0 g/dL

Ex-US submission: Mean Hb change from baseline to the average level during the Evaluation Period, defined as Week 28 until Week 36 without rescue therapy within 6 weeks prior to and during the evaluation period. This analysis will be based on the PPS population.

- The time to achieve the first hemoglobin (Hb) response defined by the primary endpoint for Ex-US or the first secondary efficacy endpoint for the US submission.
- Proportion of patient exposure time (months) with Hb ≥ 10 g/dL during Weeks 28-52, similarly analysis for the period between Weeks 28 - 36
- Mean change from baseline in Low-density lipoprotein (LDL) cholesterol averaged over Weeks 12-24
- Mean change from baseline in Hb levels between Weeks 18 to 24 in patients whose baseline hs-CRP $>$ ULN
- Average monthly IV iron use per subject during weeks 28-52
- Time to first RBC transfusion during the treatment
- Mean change in mean arterial pressure (MAP) averaged over Weeks 8-12

- Time to first exacerbation of hypertension (defined as [systolic BP ≥ 170 mmHg AND systolic BP increase from BL ≥ 20 mmHg] or [diastolic BP ≥ 110 mmHg AND diastolic BP increase from BL ≥ 15 mmHg]) during weeks 28 to 52

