11.2 ANALYSIS OF SECONDARY ENDPOINTS

The secondary endpoints are for both U.S. and Ex-U.S. submission unless otherwise specified. Once the primary hypothesis has been rejected for the primary endpoint, the secondary endpoints in the order that was specified in section 4.3 will be tested using a fixed sequence testing procedure, in order to maintain the overall two-sided type I error of 0.05. If p-value from a test is < 0.05, the claim of superiority or non-inferiority will be considered successful and the test will progress to the next comparison in sequence as follows.

Table 5 Key Secondary Endpoints Fixed Sequence Testing Procedure

Test	Variable	Comparison
1	Proportion of subjects who achieve an Hb response at two consecutive visits during the first 24 weeks of treatment, (U.S.) or the mean Hb change from baseline to the average level during the Evaluation Period, defined as Week 28 until Week 52 for Ex-U.S..	Non-inferiority of roxadustat versus EPO. The non-inferiority margin for the difference of responder analysis between groups is 0.15 The non-inferiority margin for the difference of average of Change in Hb values between groups is - 0.75 g/dL.
2	LDL cholesterol change from BL to the average of weeks 12 to 24.	Superiority of roxadustat versus EPO
3	Mean change from baseline in Hb levels between Weeks 18 to 24 in patients whose baseline CRP > ULN:	The non-inferiority with margin of - 0.75 of roxadustat versus EPO
4	Monthly IV iron (mg) use per subject during weeks 28 to 52.	Superiority of roxadustat versus EPO
45	Time to first RBC transfusion during the treatment.	Non-inferiority of roxadustat versus EPO with Non-inferiority margin of 1.8
5	Change from BL to the average MAP of weeks 8 to 12	Superiority of roxadustat versus EPO
6	Time to first exacerbation of hypertension (defined as [systolic BP \geq 170 mmHg AND systolic BP increase from BL \geq 20 mmHg] or [diastolic BP \geq 110 mmHg AND diastolic BP increase from BL \geq 15 mmHg]) during weeks 28 to 52	Superiority of roxadustat versus EPO & Non-inferiority with margin of 1.8

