11.2.1.4 Average monthly IV iron use during 28 to 52 Weeks

The average monthly IV iron use during the treatment period will be calculated for monthly intervals. The treatment period will be divided in periods of 28 days and for each of these periods the monthly mean of IV iron will be used using the following formula:

Monthly iron use for each subject = Total IV iron in mg / [(last visit date – first drug date +1)/ 28]

The average monthly iron use will be compared between the 2 treatment groups using an ANCOVA model adjust for baseline iron replete, treatment group and above-mentioned stratification factors as fixed effects. Superiority will be declared if the lower bound of the 2-

sided 95% confidence interval of the difference between Epoetin alfa and roxadustat exceeds 0.

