11.2.1.5 Mean change in mean arterial pressure (MAP) averaged over Weeks 8-12

Mean Arterial Pressure (MAP) will be calculated for each subject using the following formula: $MAP = (2/3) * DBP + (1/3) * SBP$.

Mean change from baseline in MAP will be analyzed and compared between the 2 treatment groups using an MMRM model with baseline MAP as a covariate, treatment group, visit, interaction of visit and treatment group, and above-mentioned stratification factors as fixed effects. The same strategy as that used in MMRM for Hb will be used to choose variance covariance structure. Data up to visit of Week 52 will be included in the model. The estimates for difference of MAP averaged over Weeks 8 to 12 between the two treatment groups will be generated from an estimate statement from Visit Week 8 to 12. Non-inferiority margin for the difference between groups is 1mmHg. Superiority will be declared if the upper bound of the 2-sided 95% confidence interval of the difference between roxadustat and ESA (roxadustat – ESA) is below 0.

11.2.1.6 Time to first exacerbation of hypertension over Week 28 to 52

Subject with exacerbation of hypertension is defined as meeting the following criterion:

Increase in blood pressure: An increase from baseline of ≥ 20 mm Hg systolic BP and sBP ≥ 170 mmHg or an increase from baseline of ≥ 15 mm Hg diastolic BP and dBP ≥ 100 mmHg. Increases from baseline in blood pressure are considered as confirmed by taking the mean of triplicates.

An exacerbation of hypertension is defined as an increase from baseline of ≥ 20 mm Hg systolic BP and sBP > 170 mmHg or an increase from baseline of ≥ 15 mm Hg diastolic BP and dBP > 100 mmHg).

Time to an exacerbation of hypertension in blood pressure will be analyzed and compared between the 2 treatment groups using the Cox Proportional Hazards model adjusting for baseline stratification factors. Both Non-inferiority and Superiority of roxadustat vs. ESA will be tested. The Non-inferiority margin for the difference between groups is 1.3 and the superiority margin for the difference between groups is 1. Subjects will be censored at the time of the last available blood pressure if an increase in blood pressure does not occur.

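### Time to first Hb response: the hazard-ratio non-inferiority rule names no numerator, and read as roxadustat/epoetin it passes a slower drug and fails a faster one

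*SAP*

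**What the plan says.** SAP 11.3.1.1 compares time to first Hb response between the arms with a Cox model. It sets out to test non-inferiority of roxadustat against ESA, which it says "will be declared if the upper bound of the 2-sided 95% confidence interval of the hazard ratio is less than 1.3". Protocol 8.4.3.2 gives the same rule for the same endpoint: "Non-inferiority will be declared if the upper bound of the two-sided 95% CI of the hazard ratio is less than 1.3". Neither place names the numerator or the reference arm, and nothing elsewhere in either document defines the direction of this hazard ratio.

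The event is the Hb response that serves as the Ex-US primary endpoint and the first US secondary endpoint, so a higher hazard is a better result.

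The documents place the endpoint differently in the testing order:

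- SAP 11.2 says that "the secondary endpoints in the order that was specified in section 4.3 will be tested using a fixed sequence testing procedure". In SAP 4.3, "The time to achieve the first hemoglobin (Hb) response defined by the primary endpoint for Ex-US" comes directly after the first Hb endpoint.
- Table 5, in the same SAP section 11.2, omits it.
- Its analysis sits under SAP 11.3, which opens: "The additional efficacy endpoints stated in section 4.3 will be analyzed using both the FAS".
- Protocol 8.4.3.2 lists it last among the secondary endpoints.

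**The concern.** For a desired event, non-inferiority has to rule out that roxadustat is too slow. With the ratio taken as roxadustat over epoetin, slower means below 1, so the bound that matters is the lower one. An upper-bound rule at 1.3 then limits only how much faster roxadustat may be. With the ratio taken as epoetin over roxadustat the rule is correct, but the reader has to supply that orientation.

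Time to Hb response is a stated secondary objective (Protocol 2.2, SAP 2.2), so the non-inferiority label could be wrong on a listed objective. If the Section 4.3 order governs, a wrong failure would also stop every later claim in the fixed sequence. The trial is open-label, and Protocol 8.4.5 wants the SAP finalised early to avoid bias. The direction of a pass/fail rule should therefore not be left to the programming stage.

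**Working it through.** **Which orientation do the documents imply?**

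- The hypothesis is worded as roxadustat versus ESA (SAP) and roxadustat versus epoetin alfa (Protocol).
- For time to first RBC transfusion, a harmful event, Table 5 specifies "Non-inferiority of roxadustat versus EPO with Non-inferiority margin of 1.8". A margin above 1 for a harmful event works only as roxadustat/EPO.
- For hypertension exacerbation, also harmful, SAP 11.2.1.6 states: "The Non-inferiority margin for the difference between groups is 1.3 and the superiority margin for the difference between groups is 1". The same logic applies. Table 5 gives 1.8 for this endpoint; that conflict does not change the direction.
- Where the arms are reversed, the text says so. For IV iron, SAP 11.2.1.4 requires that the lower bound of the "confidence interval of the difference between Epoetin alfa and roxadustat exceeds 0".
- Protocol 8.4.3.2 uses the same 1.3 sentence for the proportion with hypertension exacerbation, where an upper bound runs the right way. This is weaker support, because it attaches a hazard ratio to a CMH analysis of a proportion.

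**Inputs.** From the documents: 1:1 allocation; at least 600 subjects (Protocol 8.1, SAP 5.1) and about 1000 (SAP 5.1); 80% response in both arms and a responder margin of -15 points (SAP 5.1); two-sided 95% intervals (SAP 5.3). Assumed: 80% epoetin response by Week 24, proportional hazards, no loss of events to dropout.

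**The plan's own figure.** No power is given for the hazard ratio. The nearest stated figure is at least 99% for the responder endpoint. With 300 per arm, SE = √(2 × 0.8 × 0.2/300) = 0.0327 and power = Φ(0.15/0.0327 − 1.96) = 99.6%, so it reproduces.

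**Formulas**, with HR = roxadustat/epoetin and n per arm:

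- Events: E_epo = 0.80n and E_rox = (1 − 0.2^HR)n.
- SE = √(1/E_rox + 1/E_epo).
- Rule as written: P = Φ((ln 1.3 − ln HR)/SE − 1.96).
- Mirrored rule (lower bound > 1/1.3): P = Φ((ln HR + ln 1.3)/SE − 1.96).

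Example, HR 1.2 with n = 300: E_rox = 0.855 × 300 = 256.5, E_epo = 240, SE = 0.0898. As written: Φ((0.2624 − 0.1823)/0.0898 − 1.96) = 14%. Mirrored: Φ((0.1823 + 0.2624)/0.0898 − 1.96) = 99.9%.

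Probability of declaring non-inferiority:

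| True HR | 600: as written | 600: mirrored | 1000: as written | 1000: mirrored |
|---|---|---|---|---|
| 0.70 | >99.9% | 0.2% | >99.9% | 0.06% |
| 0.80 | 99.9% | 6% | >99.9% | 8% |
| 1.0 | 82% | 82% | 96% | 96% |
| 1.05 | 65% | 93% | 86% | 99% |
| 1.1 | 45% | 98% | 66% | 99.9% |
| 1.2 | 14% | 99.9% | 21% | >99.9% |

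At the mirrored margin itself (HR 0.769, 600 subjects) the rule as written passes 99.99% of the time, against 2.5% under the mirrored rule. HR 0.80 lies inside that margin, so a pass there is not a false claim; the mirrored rule would simply seldom have enough evidence to make it.

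**Highest observed HR that passes as written**, exp(ln 1.3 − 1.96 × 2/√E): 1.09 with 480 events, 1.13 with 800.

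**If the responder test comes first.** It passes with probability Φ((d + 0.15)/SE_d − 1.96), where d = (1 − 0.2^HR) − 0.80 and SE_d is unpooled:

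- HR 0.70: response 67.6% vs 80%, d = −0.124; passes 11% (600) or 15% (1000).
- HR 0.80: response 72.4% vs 80%, d = −0.076; passes 57% or 79%.
- HR 1.0 or above: passes at least 99.6%.

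The responder test therefore stops most wrong passes at HR 0.70, fewer passes at 0.80, and almost no wrong failures.

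**The case against.** The reversal is inferred. Naming roxadustat first states the hypothesis, not the ratio, and with epoetin/roxadustat the rule is correct as it stands, so the effect is then zero. Protocol 8.4.3.2 puts epoetin first for IV iron, LDL and MAP, and SAP 11.2.1.6 calls its 1.3 a margin for a difference without defining a ratio. This stands in part: the certain defect is the undefined direction, and the reversal is conditional. But the epoetin-first cases are all spelled out and this one is not, which favours the roxadustat/epoetin reading.

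The consequence is also limited. The protocol lists the endpoint last, Table 5 omits it, and SAP 11.3 treats it as additional. Only under the Section 4.3 order would a wrong failure block other claims. The hazard ratio and its interval would be reported correctly and would expose an implausible label. At equal hazards, the counterpart of the plan's equal-response assumption, both rules agree. All of this stands. It bears on severity, not on whether the rule needs correcting.

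Finally, the Section 4.3 versus Table 5 mismatch is wider than this endpoint (Table 5 also omits exposure time with Hb of at least 10 g/dL), and the missing rationale for 1.3 is a separate matter. Neither is needed to support the main point.

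**Conclusion.** The concern holds. The rule is incomplete as written, and on the reading the documents best support it runs the wrong way for a beneficial event. On that reading, with 600 subjects, it would almost always pass a drug with a response hazard 30% lower than epoetin's and would fail a drug with a 20% higher hazard about 86% of the time (100% − 14%).

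These sizes rest on the roxadustat/epoetin orientation, 80% epoetin response and proportional hazards. The direction of the error does not depend on the number of events. Treating events as fixed at 480 or 800 changes the results by about one point or less. Blocking of later claims is conditional on the Section 4.3 order. This should be fixed before analysis; it does not threaten the primary endpoints.

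**What to change.** In SAP 11.3.1.1 and Protocol 8.4.3.2, define the hazard ratio as roxadustat/epoetin alfa and require the lower bound of the two-sided 95% interval to exceed 1/1.3 = 0.77. Equivalently, define it as epoetin alfa/roxadustat and keep the upper bound below 1.3. Both forms keep the sponsor's own margin.

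Then settle the endpoint's place in the sequence. Either add it to Table 5 at a stated step, or state in SAP 4.3 and 11.2 that it lies outside the sequence, and align Protocol 8.4.3.2.

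As a secondary request, the sponsor should confirm and justify 1.3 for this endpoint, since SAP Appendix 6 covers only 0.75 g/dL and 0.15.

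Cost: one sentence in each document for the rule and one line for the sequence. There is no operational cost.

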11.3.1.2 Hemoglobin Maintenance

Hemoglobin maintenance at Weeks 28-36 will be assessed by the mean change in Hb averaged over 8 weeks of treatment at Weeks 28-36 without rescue therapy within 6 weeks prior to and during this 8-week evaluation period.

The Hb values will be used on the central laboratory values. The Weeks will be defined using the visit window defined in Appendix 1.

The mean change in Hb will be analyzed using a MMRM model described in 11.1.3.1.

11.3.1.3 Hemoglobin Long-Term Maintenance

Hemoglobin long-term maintenance will be assessed by the mean change in Hb averaged over 8 weeks of treatment at Weeks 44-52 without rescue therapy within 6 weeks prior to and during this 8-week evaluation period. The mean change in Hb will be analyzed using the MMRM model described in 11.1.3.1

The mean change in Hb averaged over 8 weeks of treatment at Weeks 96-104 will be analyzed using the MI analyses as the one for the primary efficacy endpoint of US-submission.

Hemoglobin long-term maintenance will also be assessed by % patients with average Hb level ≥ 10 g/dL during weeks 28-36; 44-52; 68-76, 96-104, etc.

To evaluate Hb maintenance by other dosing frequencies, the following summary will be provided for the subgroups of subjects treated on BIW or QW (including any frequency $< QW$ for longer than 8 weeks (i.e., ≥ 56 days):

- Average Hb values over time for every 4-8 weeks after the initiation of BIW or QW
- Average weekly dose over time for every 4-8 weeks after the initiation of BIW or QW

11.3.1.4 Hb Correction

Hb correction will be assessed using the following endpoints:

- Change in Hb at each of the selected post-dosing time points (see Table 4). Mean change in Hb at each of post-dosing time points will be presented for the 2 treatment groups. The mean change will be compared between the 2 treatment groups using the MMRM model described in 11.1.3.1.
- Change in Hb averaged over 8 weeks of treatment at Weeks 28-36, without rescue therapy within 6 weeks prior to and during this 8-week evaluation period, in subjects who have reached an Hb ≥ 11 g/dL prior to Week 28. The same MMRM model will be

used to compare the mean change from baseline in Hb within this subgroup of subjects.

- Proportion of subjects with Hb within 10-12 g/dL in U.S. and 10-13 g/dL in Ex-U.S. averaged over Weeks 28-36, without rescue therapy within 6 weeks prior to and during this 8-week evaluation period. The proportion of subjects meeting the above-mentioned criteria will be compared between the 2 treatment groups using logistic regression model adjusting for baseline Hb value as covariate with treatment group and baseline stratification factors except screening Hb values (≤ 8 g/dL vs. > 8 g/dL) as fixed effects.
- Mean change in Hb from baseline to Week 28-36, from baseline to Week 28 to 52 in the subgroup of patients with baseline CRP>ULN.
- Time to and minimum effective dose evaluation: Time to Hb ≥ 11.0 g/dL and an increase by ≥ 1 g/dL from baseline and the study drug dose will also be evaluated, with subgroup analysis by starting dose in the original protocol vs starting dose in the amended protocol.

Table 9 presents the analysis visits assigned for hemoglobin samples collection corresponding to the range of treatment days (window) during which an actual visit may have occurred. All scheduled and unscheduled hemoglobin samples that belong to each window will be taken into account.

11.3.2 Hospitalizations (including skilled nursing facility)

Hospitalizations are collected in the Hospitalization Records Form of the eCRF. For each subject, an entry will be recorded for each hospitalization. The days of hospitalization will be calculated as the sum of all hospitalizations durations in days (Date of discharge – Date of Admission + 1). In case of missing dates, the hospitalization duration will be assumed to be 5 days.

Only hospitalizations with admission dates that occur during the treatment period and up to 7 days after the last study medication date will be taken into account.

The following hospitalization-related data will be analyzed and compared between the 2 treatment groups:

- Time to first hospitalization up to Week 52- Proportion of subjects hospitalized. Time to first hospitalization or skilled nursing facility up to Week 52.
- Number of days of hospitalizations
- Number of days of medical-facility
- Number of days of hospitalizations per patient-exposure year (PEY).
- Number of days in hospital or skilled nursing facility per patient-year exposure (PEY)
- Number of days of medical-facility per subject-exposure year (PEY).

- Number of days on treatment out of hospital and skilled nursing facility up to Week 52, 7 days after Last Dose. The days will be compared between the 2 treatment groups using ANCOVA model with baseline Hb and the baseline stratification factors.

Note: Elective procedures may be excluded from analyses by using only hospitalization due to AE.

The time to hospitalization event will be compared between the two treatment groups using cox model including baseline stratification factors. The proportion of subjects hospitalized will be compared between the 2 treatment groups using logistic regression model and stratified by the baseline stratification factors. The mean number of days of hospitalization will be analyzed and compared between the 2 treatment groups using the Mantel-Haenszel mean score test adjusting for stratification factors.

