4.4 ADDITIONAL EVALUATION OF EFFICACY

The additional efficacy evaluations in this study are:

- **Hb Correction and Maintenance:**
 - Hemoglobin maintenance: Mean change from baseline in Hb averaged over 8 weeks of treatment at Weeks 28 to 36, without rescue therapy within 6 weeks prior to and during this 8-week evaluation period.
 - Hemoglobin long-term Maintenance: Mean change in Hb averaged over 8 weeks of treatment at Weeks 44-52 without rescue therapy within 6 weeks prior to and during this 8-week evaluation period.
 - Mean change from baseline in Hb averaged over the 96 to 104 weeks of treatment, without rescue therapy within 6 weeks prior to and during this 8-week evaluation period.
 - Change from baseline in Hb at each of the selected post-dosing time points.
 - Proportion of subjects with Hb ≥ 10 g/dL averaged over Weeks 28-36, without rescue therapy within 6 weeks prior to and during this 8-week evaluation period.
 - Proportion of subjects with mean Hb < 9 g/dL, 9- <10 , 10- <11 , 11- <12 , 12- <13 , ≥ 13 g/dL during Weeks 28-36
 - Proportion of patient exposure (PEY) with Hb < 9 g/dL, 9- <10 , 10- <11 , 11- <12 , 12- <13 , ≥ 13 g/dL during weeks 28 to 52
- **Hospitalizations:**
 - Time to first hospitalization (% of subjects) up to Week 52.
 - Time to first hospitalization or skilled nursing facility (% of subjects) up to Week 52
 - Number of days of hospitalizations per patient-exposure year (PEY).
 - Number of days of hospital or skilled nursing facility per PEY
 - Number of medical-facility free days (hospital, skilled nursing facility, emergency room, or overnight observation) per PEY
 - Number of days on treatment out of hospital and skilled nursing facility up to Week 52, 7 days after Last Dose.
- **Missed dialysis sessions up to Week 52**
 - Occurrence (number) of missed dialysis sessions
 - Proportion of subjects with missed dialysis sessions
 - Number of days of missed dialysis sessions per patient-exposure year (PEY)

- **Rescue Therapy Use up to Week 52:**
 - Proportion of subjects who receive RBC transfusions.
 - Number of RBC packs per patient-month exposure to study medication.
 - Roxadustat subjects: The proportion of subjects requiring ESA rescue therapy (ATC code: B03XA01)
- **Changes in Cholesterol Levels:**
 - Change at each of the protocol specified treatment time points in:
 - total cholesterol,
 - low-density lipoprotein (LDL)/high-density lipoprotein (HDL) ratio,
 - non-HDL cholesterol.

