9 STUDY MEDICATION

9.1 EXTENT OF EXPOSURE

Exposure to study medication will be summarized by treatment group in terms of treatment duration in weeks, which is calculated using the following formula: (the date of last medication taken - the date of first dose taken +1)/7.

Total weekly study drug exposure is defined as the total prescribed dose (in mg and mg/kg for Roxadustat and IU and IU/kg for EPO) of study drug administered within the week (windowed by 7-day period from Day 1).

Duration of exposure, weekly exposure and total study drug exposure will be tabulated by treatment group for the safety population.

Per administration amount and administration frequency will also be tabulated by treatment group for the safety population and PPS population.

Patient-Exposure-Year (PEY) is defined as (Last Dose Date – First Dose Date + 1)/365.25.

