16.2.6 Missing Date Information for Adverse Events

The following imputation rules only apply to the case where the start date is incomplete (i.e., partial missing) for adverse events.

Incomplete Start Date

Missing day and month

- If the year is same as the year of first day on study medication, then the day and month of the start date of study medication will be assigned to the missing fields.
- If the year is not the same as the year of first day on study medication, then January 1 will be assigned to the missing fields.

Missing month only

Treat day as missing and replace both month and day according to the above procedure.

Missing day only

If the month and year are same as the year and month of first day on study medication, then the start date of study medication will be assigned to the missing day.

If the month and year are not the same as the year and month of first day on study medication, then the first day of the month will be assigned to the missing day.

• Incomplete Stop Date

If the stop date is complete and the imputed start date as above is after the stop date, the start date will be imputed by the stop date.

If needed, the following imputation rules apply to the case where the end date is incomplete (i.e., partially missing) for adverse events. Other partial end date will not be imputed.

Missing day and month, or Missing month only

December 31 will be assigned to the missing fields.

Missing day only

The last day of the month will be assigned to the missing day.

Table 16.6-1 Imputation of the Analysis Adverse Event Start Date

Reported Date	Date of First Drug Intake	Analysis Date (Derived)
--/MM/YYYY	DD/MM/YYYY	
--/02/2008	14/02/2008	14/02/2008*
--/02/2008	14/02/2007	01/02/2008
--/02/2008	14/02/2009	01/02/2008
--/-/YYYY	DD/MM/YYYY	
--/-/2008	14/02/2008	14/02/2008
--/-/2008	14/02/2007	01/01/2008
--/-/2008	14/02/2009	01/01/2008
DD/-/----		
--/MM/----		No imputation
--/-/----		

Table 16.6-2 Imputation of the Analysis Adverse Event Stop Date

Reported Date	Analysis Date (Derived) *
--/MM/YYYY	31/MM/YYYY or 30/MM/YYYY or 29/MM/YYYY or 28/MM/YYYY
--/-/YYYY	31/12/YYYY
DD/-/----, or --/MM/----, or --/-/----	No imputation

*Death has to be taken into consideration when calculating this.

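### SAP 11.3.2 gives 5 days to every hospital stay with a missing date, even when the admission date is known and a death date or last in-hospital contact bounds the stay

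*SAP*

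**What the plan says.** SAP 11.3.2 computes the length of a stay as "Date of discharge – Date of Admission + 1" and sums over a subject's stays. For incomplete records it says: "In case of missing dates, the hospitalization duration will be assumed to be 5 days". It does not separate a missing admission date from a missing discharge date, a partial date from an absent one, or an unknown discharge from a stay that ended in death or had not ended.

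Stays are selected by admission date alone: "Only hospitalizations with admission dates that occur during the treatment period and up to 7 days after the last study medication date" are counted. The section gives no rule for a stay still open at the end of observation, and the data-handling conventions in SAP Appendix 2 (16.2) contain none.

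The durations feed comparisons between arms. "The mean number of days of hospitalization will be analyzed and compared between the 2 treatment groups using the Mantel-Haenszel mean score test". SAP 4.4 also lists hospital days per patient-exposure year (PEY) and "Number of days on treatment out of hospital and skilled nursing facility up to Week 52"; 11.3.2 compares the latter by ANCOVA. The PEY denominator is in SAP 9.1: "Patient-Exposure-Year (PEY) is defined as (Last Dose Date – First Dose Date + 1)/365.25".

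Elsewhere the SAP does bound imputed dates. For adverse event stop dates, 16.2.6 notes: "Death has to be taken into consideration when calculating this". For a missing last dose date, 16.2.8 takes the earliest of several candidates, including death and the EOT/EOS visit.

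**The concern.** Selection is by admission date, so a stay with no admission date is hard to place in the counting period at all. The 5-day rule will therefore act mainly where admission is known and discharge is not. Two kinds of stay could reach it with better information available: one that ended in death, where the death date gives the length, and one still open at last contact, where the last contact gives a minimum length. The fallback discards both.

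The two errors run in opposite directions. A very rapid death is overcounted; a long open stay, or a death late in a long stay, is undercounted. Protocol 3.1 and 6.1.2 plan for all subjects to finish treatment together at a common closeout, so some stays open at that point are foreseeable. At stake are the counts of days, which are meant to describe the burden of hospital care and would be least accurate for subjects with the longest unresolved stays.

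**Working it through.** **Inputs.** From the documents: the stay formula and the 5-day fallback (SAP 11.3.2) and the PEY formula (SAP 9.1). The stay lengths, exposure times and shares of subjects below are assumptions, because the documents give none.

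**The plan's own figure.** The 5 days is a convention. The documents contain no length-of-stay data, so there is nothing to reproduce. Under the formula it is correct only for a stay that ends 4 days after admission (4 + 1 = 5).

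**Per stay.** Bounded length = end − admission + 1, with the end set at death or at last in-hospital contact. Error = 5 − bounded length.

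| Assumed stay, discharge date missing | Bounded days | SAP days | Error |
|---|---|---|---|
| Death on day of admission | 1 | 5 | +4 |
| Death the next day | 2 | 5 | +3 |
| Death on the third day | 3 | 5 | +2 |
| Open, 14th day at last contact | at least 14 | 5 | −9 or beyond |
| Open, 30th day | at least 30 | 5 | −25 or beyond |
| Open, 60th day | at least 60 | 5 | −55 or beyond |
| Open, 90th day | at least 90 | 5 | −85 or beyond |

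In study days, admission on Day 100 and last contact in hospital on Day 160 gives 160 − 100 + 1 = 61 days observed, counted as 5. Had the same subject been discharged on Day 160, the SAP would count 61. No stay is shorter than 1 day, so the overcount is capped at 5 − 1 = 4. The rule puts no cap on the undercount.

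**Arm mean.** If a share q of an arm's subjects each have one such stay of L days, the arm's mean shifts by q × (5 − L).

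| q | L = 1 (death on admission day) | L = 30 (open) | L = 90 (open) |
|---|---|---|---|
| 1% | +0.04 | −0.25 | −0.85 |
| 5% | +0.20 | −1.25 | −4.25 |

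**Per PEY, one subject.** Rate = days ÷ (exposure days / 365.25).

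- Fatal 2-day stay, 30 days' exposure: 5 ÷ (30/365.25) = 60.9 under the SAP; 2 ÷ (30/365.25) = 24.4 bounded.
- Open 30-day stay, 180 days' exposure: 5 ÷ (180/365.25) = 10.1 under the SAP; 30 ÷ (180/365.25) = 60.9 bounded.

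**Reach.** Time to first hospitalization and the proportion hospitalized do not use duration. Neither primary endpoint uses it, nor does any endpoint in the fixed sequence of SAP Table 5.

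**The case against.** The rule acts only when a date is missing, and nothing in the documents shows that discharge dates will be missing for deaths or open stays. The Hospitalization Records Form is not included. If sites enter the death date as the discharge date, the problem does not arise for deaths. The protocol also makes gaps less likely. Inpatient hospitalization and death are serious adverse events (9.2.2), investigators are to seek discharge notes and death certificates (9.3.5), and subjects who stop drug early are followed for vital status and hospitalization until study closure unless consent is withdrawn (6.1.2.6). All of this stands. It makes the point conditional; it does not make the rule right when a date is missing.

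A fixed fallback applied alike to both arms is a recognisable simplification. The SAP's bounding rules for other variables do not by themselves make this one an error, and 16.2.3 gives a different fallback for the last dose date from 16.2.8. That is fair. The case rests on the wrong counts shown above; the other rules show only that bounding by death is already accepted practice in this SAP.

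Bounding also needs care. A subject with an unknown discharge date who dies months later must not be treated as in hospital throughout, and no passage shows a field for place of death or for an ongoing stay. Running open stays to data cut-off could add days beyond the last dose, where the PEY denominator stops, or beyond the limits of Week 52 and 7 days after last dose set for days out of hospital. Both objections stand, and the fix must respect them.

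**Conclusion.** The point holds in conditional form. Where the admission date is known and the discharge date is missing, the 5-day rule gives a wrong count for an in-hospital death unless death came on the fifth day. For an open stay it gives a wrong count whenever the observed part exceeds 5 days. The error is at most +4 days per stay in one direction and unlimited by the rule in the other. It is minor: it concerns additional endpoints without multiplicity adjustment.

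Four stronger conclusions might be inferred, and the documents do not support them:

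- That end of observation fixes the length of an open stay. It gives a minimum; the full length stays unknown.
- That the longest stays and rapid deaths will be miscounted. This depends on missing discharge dates, whose frequency is not given.
- That the comparison between arms is biased. The rule is the same in both arms, and neither the size nor the direction of any difference can be derived.
- That the primary or key secondary results are at risk. None of them uses the duration of a stay.

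The illustrations assume the stated stay lengths, one affected stay per affected subject, and that the days shown fall inside the counting window. The effect on days out of hospital assumes that these are obtained by subtracting days in hospital or facility; the SAP gives no formula.

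**What to change.** Replace the fallback in SAP 11.3.2 with a short rule. When the admission date is known and the discharge date is missing, end the stay at the earliest of:

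1. the date of death, if the record shows that the subject died during that stay;
2. the last contact at which the stay was recorded as ongoing;
3. the end of the counting window for the endpoint, which the SAP should name for each endpoint.

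Use 5 days only when no bounding date exists. State how partial dates and missing admission dates are handled, and whether the form records the date of an in-hospital death as the discharge date. Report the number of imputed stays by arm and repeat the analyses of days without them.

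The cost is a few lines of SAP text and programming, plus a check that the form or the serious adverse event records identify deaths during a stay and ongoing stays. No new data collection appears necessary if they do. One limitation remains: open stays are still counted at their minimum length.
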